3.3.7 Study Drug Exposure and Compliance

Participants' exposure to randomized study medication will be summarized with descriptive statistics by treatment for the Safety Population. Days of exposure is defined as:

$$\text{Exposure (days)} = \text{date of last dose of study drug} - \text{date of first dose} + 1$$

For those who failed to provide the date of last dose of study drug, the earliest date between the end of treatment date and the date of end of study/early termination will be used.

A summary will be provided to display counts and percentages of participants in each treatment with exposure in the following categories: <4 weeks, 4 – <8 weeks, and 8+ weeks.

Summary statistics will be presented for percent overall compliance to study medication by treatment. Counts and percentages of participants will also be tabulated by groups with overall compliance < 80%, 80% to 120%, and > 120%.

The percent overall compliance to study medication will be calculated as:

$$\text{Compliance (\%)} = \frac{(\# \text{ tablets dispensed} - \# \text{ tablets returned})}{\# \text{ expected dosing days}} \times 100$$

The number of expected dosing days = (the earliest date between the end of treatment date and the date of early termination – the date of randomization + 1).

A separate listing of derived exposure and compliance will be provided for ITT Population.

3.4 Efficacy Assessment

The mITT Population will be the primary population for the efficacy analyses. Efficacy will also be analyzed using the ITT Population, the mITT On-Treatment Population, and the PP Population as supportive analyses for selected endpoints.

LDL-C will be collected using the following two approaches:

1. LDL-C level will be calculated using the Friedewald equation unless TG ≥ 400 mg/dL or LDL-C ≤ 50 mg/dL. If TG ≥ 400 mg/dL or LDL-C ≤ 50 mg/dL, then LDL-C level will be measured directly by preparative ultracentrifugation (PUC), also referred to as beta quantification.
2. In addition, for all participants, LDL-C will be measured by PUC at Baseline (Visit 2) and at the end of the 8-week Treatment Period (Visit 5).

3.4.1 Primary Efficacy Endpoint

Primary Analysis

The primary efficacy endpoint is the percent change from Day 1 to Day 56 in LDL-C (as determined by approach 1) for each obicetrapib group compared to the placebo group. The percent change will be calculated from Day 1 (Baseline) to each measurement taken at Day 14, Day 28, and Day 56.

The mean percent change from Day 1 to Day 56 in LDL-C for each treatment is defined mathematically as μ_j , where j stands for jth treatment (j=0,1,2,3) and the subscripts 0, 1, 2, and 3 refer to the placebo, Obicetrapib 10 mg, 5 mg, and 2.5 mg group, respectively. The hypotheses

testing to the difference in the mean percent change in LDL-C from Day 1 to Day 56 between the j^{th} obicetrapib group and the placebo group is then defined statistically as following:

$$H_0: \mu_j - \mu_0 = 0, H_1: \mu_j - \mu_0 \neq 0, \text{ where } j = 1, 2, 3$$

The primary efficacy analysis of the percent change from Day 1 to Day 56 in LDL-C will be performed using a mixed model for repeated measure (MMRM) approach. The analysis will include fixed effects for treatment, visit, and treatment-by-visit interaction, along with a covariate of the Baseline value as a continuous covariate. It is to note that randomization was stratified by categories of LDL-C value (≥ 100 or < 100 mg/dL) only to ensure similar distribution of LDL-C values across all treatment. However, the MMRM model will include the original scale of the LDL-C value as a continuous covariate, not categorical.

The Restricted Maximum Likelihood estimation approach will be used with an unstructured covariance matrix. The least squares means, standard errors, and 2-sided 95% confidence intervals for each treatment group and for the pairwise comparisons of each dose of obicetrapib to the placebo group will be provided. The least squares means for the pairwise comparison and its standard error will be used for the hypothesis testing. The ratio of estimate to standard error will be approximately t distributed. The null hypothesis of no treatment effect will be rejected if the p-value, the probability of obtaining the observed or more extreme value of t statistic under the null hypothesis, is less than or equal to 0.05.

In order to maintain the overall alpha level on the primary endpoint, the hypothesis testing will be performed sequentially at the 2-sided alpha=0.05 significance level. The first comparison will be the 10 mg obicetrapib group versus placebo; if significant, comparison of the 5 mg obicetrapib group versus placebo will be performed, followed by the 2.5 mg obicetrapib group versus placebo. Hypothesis testing will proceed in this hierarchical step-down fashion until a comparison is not significant. At that point, all remaining sequential tests will be deemed not significant.

The MMRM approach will include all available assessments of percent change in LDL-C from Baseline to Day 14, Day 28, and Day 56. The model assumes the data are missing at random (MAR). If any data are missing, the model will use all information from the other time points as well as Baseline covariate values to estimate the mean treatment difference at the given time point. No imputation of missing data will be performed for the primary efficacy endpoint analysis.

In order to address the effect of intercurrent events, "While-on-Treatment Strategies" will be employed¹. For participants who are withdrawn from the study because of the use of an excluded medication and/or procedure, data occurring after the intercurrent event of excluded medications use will be excluded from the primary analysis. For participants who are withdrawn from the trial, data occurring after the intercurrent event of failure to adhere to treatment dosing will be excluded from the primary analysis. Failure to adhere to treatment dosing will be defined as study drug compliance <75% at the time of study withdrawal.

The MMRM analysis will be implemented using SAS[®] Proc Mixed. Example SAS code can be found below:

Note:

USUBJID = unique subject identifier

TREATMENT = 0 (Placebo), 1 (2.5 mg obicetrapib), 2 (5 mg obicetrapib), 3 (10 mg obicetrapib)

VISIT = Visit

BASE = Baseline value

PCHG = Percent change from Baseline

proc mixed;

class USUBJID TREATMENT VISIT;

model PCHG = TREATMENT BASE VISIT TREATMENT*VISIT / solution cl;

repeated VISIT / TYPE=UN sub=USUBJID;

lsmeans VISIT*TREATMENT / cl diffs;

run;

Values, changes from Baseline, and percent change from Baseline of LDL-C will be summarized using descriptive statistics at scheduled visits and Baseline by treatment group.

Counts and percentages of participants will be summarized by treatment for each type of data pattern. There will be 16 data patterns for four time points (Baseline, Day 14, Day 28 and Day 56) each having two possible outcomes (LDL-C data reported or missing).

Waterfall plot of percent change in LDL-C from Baseline to each scheduled visit will be created. Line plot of the mean (+/- 2 * SE) and the median (and IQR) percent change in LDL-C from Baseline to each scheduled visit will be created. Figures will be created for LDL-C values collected using two approaches described above.

The main analyses for the primary efficacy endpoint will be repeated for the ITT Population, the mITT On-Treatment Population, and PP Population.

Sensitivity Analyses

Three sensitivity analyses will be performed for the primary efficacy endpoint:

1. MMRM with imputation
2. Analysis covariance (ANCOVA)
3. ANCOVA using LDL-C by PUC

All sensitivity analyses will be conducted on the mITT Population.

Sensitivity Analysis 1

The first sensitivity analysis will be performed in two steps. In the first step, missing data will be assumed missing not at random (MNAR). Missing data at Days 14, 28 and 56 will be imputed using multiple imputation methodology in two steps. Initially, 25 data sets will be imputed for non-monotone missing values in the original dataset. In the second step the remaining monotone missing values in the 25 data sets will be imputed based on the observations in the Placebo group. Upon completion of the trial, if the percentage of cases with incomplete data is larger than initially anticipated then the number of imputations will be increased for the final analysis.

The variables for the imputation model will consist of LDL-C values from Baseline and Days 14, 28 and 56. For each imputation dataset, the percent change from Baseline to Day 56 will be analyzed using the MMRM model described for the primary analysis. The results from these 25 analyses will be combined using Rubin's method to construct the treatment estimates using the parameter estimates and associated standard errors. Similarly, the difference of the adjusted

treatment means (the three doses of obicetrapib therapy – Placebo) will be presented with the associated standard error and 95% confidence interval. Randomly chosen seed numbers will be selected for the analysis and will be retained.

Example SAS code to create a dataset for non-monotone missing values is shown below:

```
*****
```

Note:

non-MONOTONE missing values

TREATMENT = 0 (Placebo), 1 (2.5 mg obicetrapib), 2 (5 mg obicetrapib), 3 (10 mg obicetrapib)

LDLC_BASE = LDL_C Baseline value

LDLC_Day14 = LDL_C value at Day 14

LDLC_Day28 = LDL_C value at Day 28

LDLC_Day56 = LDL_C value at Day 56

```
proc mi data=LDLC_Wide seed=20220101 out=LDLC_25MCMC n impute=25;
```

```
var TREATMENT LDLC_base LDLC_Day14 LDLC_Day28 LDLC_Day56;
```

```
mcmc impute=monotone chain=multiple;
```

```
run;
```

In the second step, the remaining monotone missing values will be imputed. Example SAS code to complete this step is shown below:

```
*****
```

Note:

MONOTONE missing values

TREATMENT = 0 (Placebo), 1 (2 mg obicetrapib), 2 (5 mg obicetrapib), 3 (10 mg obicetrapib)

LDLC_BASE = LDL_C Baseline value

LDLC_Day14 = LDL_C value at Day 14

LDLC_Day28 = LDL_C value at Day 28

LDLC_Day56 = LDL_C value at Day 56

```
proc mi data= LDLC_25MCMC seed=810456 out= LDLC_Mono n impute=1 simple;
```

```
by _Imputation;
```

```
class TREATMENT;
```

```
monotone method=reg;
```

```
mnar model (LDLC_Day14 LDLC_Day28 LDLC_Day56 / modelobs=(TREATMENT="0"));
```

```
var LDLC_base LDLC_Day14 LDLC_Day28 LDLC_Day56;
```

```
run;
```

For each imputation dataset, the percent change from Baseline to Day 14, Day 28 and Day 56 will be analyzed using similar MMRM approach. Then the parameter estimates will be combined using Rubin's method. Example SAS code to combine the parameter estimates is shown below:

```
*****
```

Note:

MIANALYZE to combine imputations

```
*****
```

```
proc mianalyze parms(classvar=full)=mixLSM;
```

```
class TREATMENT;
```

```
modeleffects TREATMENT;
ods output parameterestimates=mi_LSM;
run;
proc mianalyze parms(classvar=full)=mixDIFF;
  class TREATMENT;
  modeleffects TREATMENT;
  ods output parameterestimates=minus_mi_DIFF;
run;
*****
```

Sensitivity Analysis 2

In the second sensitivity analysis, the percent change from Day 1 to Day 56 in LDL-C, via approach 1, for the obicetrapib groups compared to the placebo group will be analyzed using an Analysis of Covariance (ANCOVA) model with fixed effects of treatment group and the Baseline LDL-C value as a continuous covariate. The least squares means, standard errors, and 2-sided 95% confidence intervals for each treatment group, for the pairwise comparisons of three obicetrapib will be provided. The treatment comparison will be performed using a 2-sided test at the $\alpha = 0.05$ level of significance. No imputation of missing data will be performed for this sensitivity analysis.

Example SAS code can be found below:

```
*****  
Note:  
USUBJID = unique subject identifier  
TREATMENT = 0 (Placebo), 1 (2.5 mg obicetrapib), 2 (5 mg obicetrapib), 3 (10 mg  
obicetrapib)  
BASE = Baseline value  
PCHG = Percent change from Baseline  
*****
```

```
proc glm data=LDL_C;
  class TREATMENT;
  model PCHG = TREATMENT BASE / ss1 ss3;
  means TREATMENT;
  lsmeans TREATMENT / cov stderr pdiff cl;
  estimate " 2.5 mg obicetrapib - Placebo" TREATMENT -1 1 0 0;
  estimate " 5 mg obicetrapib - Placebo" TREATMENT -1 0 1 0;
  estimate " 10 mg obicetrapib - Placebo" TREATMENT -1 0 0 1;
run;
*****
```

Sensitivity Analysis 3

In the final sensitivity analysis, the percent change from Day 1 to Day 56 in LDL-C will be assessed where the LDL-C values were determined by approach 2. The percent change from Day 1 to Day 56 in LDL-C by PUC for the obicetrapib groups compared to the placebo group will be analyzed using an ANCOVA similar to the model described in the second sensitivity analysis. No imputation of missing data will be performed for this sensitivity analysis.

Values, changes from Baseline, and percent change from Baseline of LDL-C by PUC will be summarized using descriptive statistics at scheduled visits and Baseline by treatment group.

Counts and percentages of participants will be summarized by treatment for each type of data pattern. There will be four data patterns for two time points (Baseline and Day 56) each having two possible outcomes (LDL-C data reported or missing).

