3.2 Analysis Populations

3.2.1 *Intent-to-Treat (ITT) Population*

The Intent-to-Treat (ITT) Population will include all participants randomized into the study. Treatment classification will be based on the randomized treatment.

3.2.2 *Modified Intent-to-Treat (mITT) Population*

The Modified ITT (mITT) Population will include all participants in the ITT Population who receive at least 1 dose of any study drug and have a Baseline value for the LDL-C assessment. Any efficacy measurement obtained during the Safety Follow-up Visit after a participant

permanently discontinues the study drug or after a participant receives an excluded medication and/or procedure will be removed from the mITT analysis. Treatment classification will be based on the randomized treatment. The mITT Population will be used for the primary analysis of all efficacy endpoints.

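### Does the Friedewald-to-PUC switch in the primary LDL-C value call for a different primary measurement?

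*SAP*

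**What the plan says.** SAP Section 3.4 describes two ways of obtaining LDL-C. Approach 1 is the Friedewald calculation with two exceptions, triglycerides of 400 mg/dL or more and LDL-C of 50 mg/dL or less; in either case "LDL-C level will be measured directly by preparative ultracentrifugation (PUC), also referred to as beta quantification". Approach 2 is PUC for every participant, at Visits 2 and 5 only. Section 3.4.1 states the primary endpoint as "percent change from Day 1 to Day 56 in LDL-C (as determined by approach 1) for each obicetrapib group compared to the placebo group".

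Three post-baseline visits enter the primary model: "The MMRM approach will include all available assessments of percent change in LDL-C from Baseline to Day 14, Day 28, and Day 56". Sensitivity Analysis 2 is an ANCOVA of the Day 56 percent change by approach 1. In Sensitivity Analysis 3, "the percent change from Day 1 to Day 56 in LDL-C will be assessed where the LDL-C values were determined by approach 2", with a similar ANCOVA. Both are on the mITT Population without imputation. The section adds: "Figures will be created for LDL-C values collected using two approaches described above".

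Protocol Section 7 gives the same measurement rule and the same additional PUC samples, but does not say which value is primary. The SAP settles that.

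**The concern.** Protocol Section 4.1 requires LDL-C above 70 mg/dL and triglycerides below 400 mg/dL at Screening, so almost every Baseline value will be Friedewald. Protocol Section 1.3 reports an incremental reduction of up to 45.3% on 10 mg with statins, so many treated participants should fall to 50 mg/dL or below by Day 56. Their percent change then has a PUC numerator over a Friedewald denominator, while nearly all placebo participants have Friedewald over Friedewald. Which assay is used depends on the response, and so on arm and dose.

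If the two methods disagree, the estimated effect of each dose and the comparison between doses could shift, which matters in a dose-finding trial. A same-assay percent change is available at exactly the two visits that define the endpoint, yet it enters inference only as a sensitivity analysis. Naming it as primary looks almost free.

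**Working it through.** **The plan's own figures.** Inputs from SAP Section 2.2.4: 25 evaluable per arm, difference 30 points, SD 25, two-sided 0.05, dropout 7%.

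- Standard error (SE) of a contrast with placebo: 25 × √(2/25) = 7.07 points; 95% half-width 14.2.
- Power (two-sample noncentral t, 48 df): 98.6%, which agrees with the stated >90%.
- Enrolment: 25/0.93 = 26.9, so 27 per arm and 108 in total, as stated.

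**Share of Day 56 values read by PUC.** Assume the percent change is normal with SD 25 and all participants share one Baseline value. The share is Φ((50 − base × (1 − reduction)) / (0.25 × base)). For Baseline 85 mg/dL and a 30% reduction this is Φ((50 − 59.5)/21.25) = Φ(−0.447) = 33%.

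| Assumed Baseline (mg/dL) | 30% reduction | 45% reduction | Placebo (0%) |
|---|---|---|---|
| 85 | 33% | 56% | 5% |
| 100 | 21% | 42% | 2% |
| 120 | 13% | 30% | 1% |

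The imbalance is real under any plausible Baseline.

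**Effect on the contrast.** The documents give no Friedewald–PUC difference, so it has to be assumed. Ten forms were simulated: ±5 mg/dL; ±8 mg/dL; ±8%; ±8 mg/dL at or below 50 tapering to zero at 100; ±10 mg/dL at or below 50 only. With three Baselines and two reductions this makes 60 cases. The departure is (active − placebo) under the method, minus (active − placebo) with PUC at both visits. A positive value means the benefit looks smaller.

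| | Approach 1 | Friedewald throughout |
|---|---|---|
| Range, points | −1.2 to +2.6 | −6.2 to +6.0 |
| Median size, points | 0.78 | 2.29 |

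- Largest departure under approach 1: 2.55/7.07 = 0.36 SE.
- In all 48 non-proportional cases the switch brings the result closer to PUC/PUC than Friedewald throughout. For example, at Baseline 85, a 45% reduction and Friedewald 8 mg/dL high, the departure falls from +3.85 to +0.50.
- In the 12 proportional cases Friedewald throughout gives 0, and the switch creates −1.2 to +1.9.
- The difference between a 45% dose and a 30% dose shifts by −0.5 to +0.9 points; 0.86/7.07 = 0.12 SE.

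**Harsher assumptions.** The 0.36 SE is the largest of these scenarios and not a ceiling.

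- Simple product of share and difference: 0.5 × 5/90 = 2.8 points (0.39 SE); 0.6 × 8/90 = 5.3 points (0.75 SE).
- The same ten forms with SD 15: up to +4.3 points. The SE is then 15 × √(2/25) = 4.24, so this is about 1 SE.
- Friedewald reading 2 to 8 mg/dL low on active drug only (mean Baseline about 100, SD of change 15): −1.1 to −6.9 points. The largest is 6.94/7.07 = 0.98 of the plan's SE, or 1.6 of the SE of 4.24 that goes with SD 15. It occurs at a 20% reduction, where few values are switched. At 45%, with more switched, the same 8 mg/dL gives −3.2. The disagreement left above 50 mg/dL drives this result; the switch does not.

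**Power if the 30-point difference shrank.** The normal approximation gives 97.0% after a loss of 0.4 SE, 94.3% after 0.7 SE and 91.7% after 0.9 SE (90.6% by noncentral t). In the drug-only case the benefit looks larger, so power is not what would suffer there.

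**The case for a change.** The best case for a change is about the headline estimate. Doses are chosen on the size of the effects, and once the data are unblinded nobody can neutrally decide whether the approach-1 or the PUC result leads. PUC is already planned for everyone at Visits 2 and 5, the SAP gives no reason for preferring approach 1, and no table shows how many values were switched in each arm.

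The facts in this stand; the remedy is less simple than it appears.

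- **Keep the mixed model with PUC/PUC at Day 56.** Days 14 and 28 have only approach 1, so one model would hold two assays across visits, and a missing Day 56 value would be predicted from visits on the other assay.
- **Make the PUC ANCOVA primary.** This abandons the mixed model in Protocol Section 9.2.1.1 and the information from earlier visits.
- **Either way, other parts must be redefined.** Early termination values windowed to Week 8 (Days 43 to 70) have no scheduled PUC. If every dropout were affected, this is 27 × 0.07 = 1.9 participants per arm. Sensitivity Analysis 1 relies on a single series: "The variables for the imputation model will consist of LDL-C values from Baseline and Days 14, 28 and 56". The mITT Population must "have a Baseline value for the LDL-C assessment", and the PP and mITT On-Treatment Populations also need a Day 56 value, so membership would depend on the assay named.

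The worry about choosing afterwards is met because the SAP names approach 1 as primary and the PUC analysis as sensitivity in advance.

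**Conclusion.** No change is needed. The hybrid rule is prespecified without ambiguity and uses the only LDL-C series scheduled at every visit in the primary model. In most level-dependent scenarios the switch reduces the error that Friedewald alone would leave.

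The size rests entirely on assumed assay differences. It is about 0 to 0.4 SE (up to about 3 points against an SE of 7.1) if the disagreement depends on LDL-C level and the SD is 25. It is about 1 SE of the plan's contrast, some 7 points, if the disagreement arises only on drug. Power stays above 90% for losses of up to 0.9 SE.

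If the true disagreement is at the harsher end, the plan will show it. Sensitivity Analyses 2 and 3 fit similar ANCOVAs in the same population for every dose and differ mainly in the assay. They share nearly all participants, so much of the between-participant variation cancels when they are compared. Sensitivity Analysis 2 also links the primary mixed model to the PUC result, separating a change of model from a change of assay. A count of PUC-read values by arm and visit, and a sentence on why approach 1 leads, would help the reader of the study report but would alter no result. Making PUC primary is a defensible preference, not a correction.

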5.3 Randomization and Blinding

Participants who meet all eligibility criteria will be randomized into the study. Participants will be randomized in a 1:1:1:1 ratio to the 2.5 mg obicetrapib, 5 mg obicetrapib, 10 mg obicetrapib, or placebo treatment groups. At randomization, participants will be stratified according to their Screening Visit (Visit 1) LDL-C level (≥100 or <100 mg/dL). An automated interactive response technology (IRT) system will be used to assign the participant to 1 of the 4 treatment groups, and visits will be registered in the IRT for Screening and Visits 1 through 5 as well as Early Termination, if applicable.

Participants, Investigators, the CRO, and the Sponsor will be blinded to all lipid results from Day 1 (Visit 2) for the first participant and continuing to database lock in order to protect blinding to treatment assignment.

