9.2.5 Sample Size Determination

A sample size of at least 100 evaluable participants (i.e., 25 participants per treatment group) will provide >90% power to detect a 30% difference in LDL-C reduction at Day 56 (SD of 25%) for each of the obicetrapib groups compared to the placebo group at a 2-sided significance level of 0.05.

The sample size for this study was determined in order to provide sufficient power for the analyses of the primary efficacy endpoint described in Section 7. Therefore, assuming a dropout rate of approximately 7%, an estimated enrollment target of approximately 108 participants (i.e., 27 participants per treatment group) is planned for this study. This sample size will also contribute sufficient participant exposure and safety data.

Participants will be stratified according to their Screening Visit (Visit 1) LDL-C levels (≥100 or <100 mg/dL).

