3.1.2 Analysis Visits

Scheduled visits will be assigned to analysis visits as recorded on the case report form (CRF). Early termination visits will be assigned to analysis visits according to the following visit windows:

Analysis Visit	Target Analysis Day	Low Analysis Day	High Analysis Day
Day 1	1	NA	NA
Week 2	14	2	21
Week 4	28	22	42
Week 8	56	43	70
Safety Follow-up	84	71	

Unscheduled visits recorded on the CRF will not be re-assigned and remain labeled as unscheduled.

3.1.3 *Definition of Baseline*

Unless otherwise stated, Baseline will be defined as the last measurement prior to the first dose of study drug.

3.1.4 *Summary Statistics*

Categorical data will generally be summarized with counts and percentages of participants. The denominator used for the percentage calculation will be clearly defined. Continuous data will generally be summarized with descriptive statistics including n (number of non-missing values), mean, median, standard deviation, minimum, and maximum.

3.1.5 *Evaluation of Site Effect*

This is a multi-center study. Sites will not be pooled for any planned inferential analysis but may be pooled for subgroup analysis to assess the heterogeneity of treatment effects among pooled sites. The final pooling algorithm, if needed, will be specified before treatment unblinding and will be provided as an addendum to the SAP. Additionally, a review of by-site effects will be performed in the context of data listing review.

3.1.6 *Handling of Dropouts and Missing Data*

Date Values

In cases of incomplete dates (e.g. adverse event (AE), concomitant medication, and medical history start and/or stop dates), the missing component(s) will be assumed as the most conservative value possible. For example, if the start date is incomplete, the first day of the month will be imputed for the missing day and January will be imputed for the missing month. If a stop date is incomplete, the last day of the month will be imputed for the missing day and December will be imputed for the missing month. Incomplete start and stop dates will be listed as collected without imputation.

Date imputation will only be used for computational purposes such as treatment-emergent status. Actual data values, as they appear in the original CRFs, will be presented within the data listings.

Non-Date Values

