3.4.2 Secondary Efficacy Endpoints

Similar MMRM models as described for the primary efficacy analyses will be used to analyze the secondary efficacy endpoints based on the mITT Population. No adjustment will be made for multiplicity in testing the secondary efficacy endpoints. Nominal p-values will be provided when applicable.

Values, changes from Baseline, and percent change from Baseline of each lipid profile will be summarized using descriptive statistics at scheduled visits and Baseline by treatment group. The following endpoints will be examined:

- Percent change from Day 1 to Day 56 in ApoB for each obicetrapib group compared to the placebo group;
- Percent change from Day 1 to Day 56 in non-HDL-C for each obicetrapib group compared to the placebo group; and
- Percent change from Day 1 to Day 56 in HDL-C for each obicetrapib group compared to the placebo group.

Waterfall plot of percent change in ApoB from Baseline to each scheduled visit will be created.

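### Randomisation is stratified on Screening LDL-C, but the efficacy models adjust only for the separate Day 1 LDL-C, so a little precision is lost and SAP 3.4.1 blurs the two measurements

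*SAP*

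**What the plan says.** **Stratification.** Protocol 5.3: "At randomization, participants will be stratified according to their Screening Visit (Visit 1) LDL-C level", with a cut at 100 mg/dL. SAP 2.2.2 repeats this. Day 1 (Visit 2) is a separate visit up to two weeks after Screening, and Protocol Appendix A schedules a fasting lipid profile at both.

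**Baseline.** SAP 3.1.3: "Baseline will be defined as the last measurement prior to the first dose of study drug". SAP 3.4.1 calculates percent change from Day 1 and labels that value Baseline.

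**Primary model.** SAP 3.4.1 says the stratification was done only to balance LDL-C across arms, and then that "the MMRM model will include the original scale of the LDL-C value as a continuous covariate, not categorical". The code is "model PCHG = TREATMENT BASE VISIT TREATMENT*VISIT / solution cl". It contains neither the stratum nor Screening LDL-C. The two ANCOVA sensitivity models have treatment and Baseline LDL-C only.

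**Secondary models.** SAP 3.4.2: "Similar MMRM models as described for the primary efficacy analyses will be used to analyze the secondary efficacy endpoints".

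**Where Screening LDL-C appears.** It is used for eligibility (Protocol 4.1, criterion 3), for the strata, and, as the stratum, in the baseline table (SAP 3.3.4).

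**The concern.** An analysis normally reflects the factors used to restrict randomisation. A continuous version of the stratification variable is a good substitute for its categories, and the SAP sentence seems to rely on that argument. But the strata come from the Visit 1 draw and the covariate from the Visit 2 draw. LDL-C varies within a person, so some participants will be on one side of 100 mg/dL at Screening and on the other at Day 1.

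The second draw also carries information. The outcome is 100 × (Day 56 − Day 1) / Day 1, so chance error in the single Day 1 value enters both the numerator and the denominator. Adjusting for Day 1 removes part of that. A second pre-treatment value helps to separate a participant's usual level from the error on the day, and so predicts percent change beyond Day 1 alone. Leaving it out makes the residual variance, and hence the standard errors, slightly larger than they need be.

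If BASE in the secondary models is each analyte's own baseline, the models for ApoB, non-HDL-C and HDL-C contain no LDL-C term at all, and the randomisation factor is then wholly unadjusted.

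**Working it through.** **1. Inputs from the documents.** Testing: "the hypothesis testing will be performed sequentially at the 2-sided alpha=0.05 significance level". Size: "A sample size of at least 100 evaluable participants (i.e., 25 participants per treatment group"). Planned effect and SD: it "will provide >90% power to detect a 30% difference in LDL-C reduction at Day 56 (SD of 25"%). Dropout is about 7%, with 108 enrolled.

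**2. The plan's own figures.**
- Standard error of a pairwise difference: 25 × √(2/25) = 7.07 points.
- Power at 30 points, normal approximation: 30/7.07 = 4.24, and Φ(4.24 − 1.96) = 98.9%. Noncentral t gives 98.7% on 95 df (100 participants less four arm means and one slope). The stated >90% is confirmed; 15 per arm would be enough for 90%.
- Enrolment: 25/0.93 = 26.9, so 27 per arm; 100/0.93 = 107.5, so 108. Confirmed.

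**3. Precision as planned.** Half-width of the 95% CI = t(0.975, 95 df) × 7.07 = 1.985 × 7.07 = 14.0 points. This takes 25 as the residual SD with Day 1 LDL-C already in the model; the documents do not say whether the planned SD is before or after adjustment.

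**4. How much could be gained.** The documents give no within-person variability and no Screening-to-Day 1 correlation, so this step rests on assumptions.
- Simulation with usual LDL-C 105 (SD 25) mg/dL, Screening >70, within-person CV 8-15% and response SD 12-22% implies a Screening-Day 1 correlation of 0.62-0.85. Residual variance falls by about 1-5% with the stratum and about 4-10% with continuous Screening LDL-C.
- A second simulation used mean 100, SD 25, between-visit correlation 0.5-0.9 and 2,000 stratified trials per scenario, with a complete-data Day 56 ANCOVA standing in for the MMRM. Standard errors were 0.3-3.4% smaller with the stratum and 1.6-10% smaller with continuous Screening LDL-C. Where the SD of percent change was near the planned 25 (25 to 28), the gains were 0.3-2.2% and 1.6-4%.

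The direction was the same in every scenario.

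**5. Effect on the interval.** If the added term cuts residual variance by a fraction R², the half-width becomes t(0.975, 94 df) × 7.07 × √(1 − R²), with one df spent.

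| Added term | R² | Half-width (points) |
|---|---|---|
| None | 0 | 14.04 |
| Stratum, low | 0.01 | 1.986 × 7.07 × 0.995 = 13.97 |
| Stratum, high | 0.05 | 1.986 × 7.07 × 0.975 = 13.68 |
| Screening LDL-C, low | 0.04 | 1.986 × 7.07 × 0.980 = 13.76 |
| Screening LDL-C, high | 0.10 | 1.986 × 7.07 × 0.949 = 13.32 |

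**6. Effect on power.** At 30 points, 98.7% becomes 99.1% at R² = 0.05 and 99.3% at R² = 0.10. At 20 points, 79.9% becomes 81.9% and 83.9%.

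**7. Validity.** With no treatment effect, the planned model rejected in 3.5-4.9% of simulated trials at nominal 5%, so type I error is not inflated.

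**The case against.** The strongest reply is that this is a disclosed, prespecified choice with almost no consequence. Much of that stands.

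- **A reader might infer that the SAP misstates its covariate.** It does not say that the covariate is the Screening value. It says stratification was for balance and that LDL-C enters on its original scale. Taking Day 1 LDL-C as a stand-in for the stratum is the natural reading but not an explicit claim, so the sentence needs clarifying rather than refuting.
- **A reader might infer that Screening LDL-C goes unused.** It decides eligibility, defines the strata and feeds the baseline table. It could even become Baseline for a participant with no Day 1 value, under the last-measurement rule. It is absent only as a term in the efficacy models.
- **A reader might infer a Protocol-SAP conflict.** There is none: Protocol 9.2.1.1 also lists only the Baseline value as a covariate.
- **A reader might infer that the change would make dose-against-dose comparisons precise enough.** It would not. An interval of ±14.0 points becomes ±13.3 at best, and the planned hypotheses compare each dose with placebo.
- **The size is assumed.** The simulations applied the >70 mg/dL cut but not the exclusion of patients already at their lipid targets (Protocol 4.2, criterion 3), which would reshape the distribution around 100 mg/dL. Any gain on the secondary endpoints was not calculated.
- **A reader might extend the point to the single Baseline slope across visits.** That is a separate modelling preference, and nothing calculated here supports changing it.

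What remains is that a prognostic value already collected on everyone, and used to restrict the randomisation, is left out for a reason that does not quite apply to it.

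**Conclusion.** The point holds as a small, cheap gain in efficiency and a correction to the stated rationale. Day 1 LDL-C is a different measurement from the one that defined the strata, and neither the stratum nor Screening LDL-C is in any efficacy model.

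Under the assumed within-person variability, the stratum would cut residual variance by about 1-5% and continuous Screening LDL-C by about 4-10%. That takes the half-width from 14.0 points to between 13.7 and 14.0, or between 13.3 and 13.8, respectively. With the SD of percent change near the planned 25, the second simulation puts the gain for continuous Screening LDL-C at no more than about 4% of the standard error. These ranges are illustrative, not bounds, because the documents supply none of the correlations.

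The planned analysis is unbiased on this point, its type I error is not inflated, and power at 30 points is about 98.7% before any change. No planned conclusion depends on the omission, and the documents do not support a stronger reading.

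**What to change.** Before unblinding:

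1. Add Screening LDL-C as a continuous fixed effect to the primary MMRM and to the ANCOVA models of Sensitivity Analyses 2 and 3. If the sponsor prefers, use the stratum as randomised (≥100 / <100 mg/dL); it recovers less. Sensitivity Analysis 1 reuses the MMRM, so its imputation variables should include the same term.
2. Carry the randomisation factor into the secondary models, and say explicitly which baseline value BASE denotes there.
3. Rewrite the SAP 3.4.1 sentence to say that BASE is the Day 1 (Visit 2) value and that the strata were formed from Screening (Visit 1) LDL-C. If the stratum is still left out, say so and justify it.
4. List the added term in SAP Section 5, because the Protocol model names only the Baseline covariate.

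The cost is one degree of freedom of about 95, one extra term in the model code, and SAP wording. No new data, visits or participants are needed.
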